#### ***14.2.5.4. Number and duration of hospitalizations***

Hospitalizations for cardiovascular events will be characterised by:

- Hospitalization for AF treatment
- Hospitalization for worsening of heart failure
- Hospitalization for myocardial infarction

The number of hospitalizations (for cardiovascular events, for thromboembolic stroke and for all causes) will be described by treatment group and compared using Cochran-Mantel-Haenszel test stratified by country.

The duration of hospitalizations for cardiovascular events, for thromboembolic stroke and for any cause will be described by treatment group and compared using a non-parametric analysis of covariance (based on ranks) adjusted for country.

#### ***14.2.5.5. Cardioversion assessment***

The number of spontaneous cardioversion before visit 3, of successful cardioversion (including number of shocks distribution) at visit 3 and the number of patients needing another cardioversion after initial ECV will be described by treatment group and compared using Cochran-Mantel-Haenszel test stratified by country.

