### **Study objectives**

The primary objective of the study is to assess the efficacy of F373280 on the maintenance of sinus rhythm after direct ECV in patients with persistent AF and chronic heart failure.

The secondary objectives of the study are to assess:

- the efficacy of F373280 on the efficiency of direct ECV
- the effect of F373280 on echocardiographic parameters
- the safety and tolerability of F373280

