**V5 et V8 were cancelled in the amendment PA05**

## 7. ANALYSIS SETS

The following analysis sets will be defined:

- **The Screened patients Set** which consists of all patients who have signed an informed consent,
- **The Randomised Patients Set** which consists of all patients who have signed an informed consent, and are assigned a treatment number,
- **The Safety Set** composed of all randomised patients having taken at least one dose of the study treatment. This set will be used to perform analyses of Safety.
- **The Full Analysis Set (FAS)** composed of all randomised patients having received at least one dose of the study treatment and with a successful cardioversion observed at visit 3. A successful cardioversion will be defined as either spontaneous cardioversion before V3 or successful ECV performed at V3 (early relapse within the observation period after ECV will be considered as non successful). This set will be used to perform analyses of Efficacy.
- **The Per Protocol Set (PP)** which is the subset of the Full Analysis Set composed of all FAS patients without any major protocol deviation or other source of bias for primary criteria analyses. This set will be used to perform the supportive analysis of the primary efficacy criterion.

Patients from Randomised Patients Set, Safety Set, Full Analysis Set or PP set will be analysed as treated (*ie* as treatment actually received at the randomisation). In case of error of treatment dispensation during the study period, the assignment of patient treatment group will be discussed during the data review meeting.

Randomised patients not treated will be analysed as randomised (*ie* as treatment allocated at the randomisation).

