## 14.2. SECONDARY CRITERIA

All secondary analyses will be performed on the FAS.

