## 18. CHANGES SINCE PROTOCOL REDACTION

The following modifications were made to statistical analyses compared to those envisaged in the Version 9 of the protocol dated December 6th, 2016:

- predictive probability of success and conditional power for primary efficacy criterion will be added
- subgroups analyses for primary criterion will be added
- ROC curves for primary criterion exploratory analyses according to DHA will be added
- the secondary criteria analyses repeated on the PP set will not be performed
- the secondary criteria were extended to the flutter detection as the primary efficacy criterion
- VS parameters in standing positions will not be analysed (only provided in individual data listings)
- Frequencies on the ECG clinical interpretation will not be presented (not collected)- Analysis of TEAEs occurrences by MedDRA SOC, PT, seriousness and Treatment Group will be added as per EudraCT requirement

**Note:** the Full Analysis Set definition was clarified with the definition of successful cardioversion as either spontaneous cardioversion before V3 or successful ECV performed at V3.

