11.4.1.2	Time to first AF recurrence/flutter emergence less than 10 minutes - Cox analysis [FAS]	11_4_1_2_4_3_AFless10_cox.RTF
11.4.1.2	Time to first symptomatic AF/Flutter - Survival curves and Logrank test [FAS]	11_4_1_2_4_1_symptAF_KM.gif
11.4.1.2	Time to first symptomatic AF/Flutter - KM summary [FAS]	11_4_1_2_4_2_symptAF_KM.RTF
11.4.1.2	Time to first symptomatic AF/Flutter - Cox analysis [FAS]	11_4_1_2_4_3_symptAF_cox.RTF
11.4.1.2	Maximum EHRA score- CMH [FAS]	11_4_1_2_5_ehra.RTF
11.4.1.2	Frequency of symptoms - -[FAS]	11_4_1_2_6_symptfreq.RTF
11.4.1.2	Presumed arrhythmia - -[FAS]	11_4_1_2_7_arrhy.RTF
11.4.1.2	Number of symptomatic AF recurrence/Flutter emergence - [FAS]	11_4_1_2_8_nb_symptrecu.RTF
11.4.1.2	Number of hospitalizations- [FAS]	11_4_1_2_9_1_nb_hospit.RTF
11.4.1.2	Duration of hospitalizations- [FAS]	11_4_1_2_9_2_dur_hospit.RTF
11.4.1.2	Cardioversion assessment- [FAS]	11_4_1_2_10_cardiov_asses.RTF
11.4.1.2	Echocardiographic parameters values and changes over time- [FAS]	11_4_1_2_11_echoparam_assess.RTF
11.4.1.2	Values and changes from baseline for red blood cell concentration of DHA [FAS]	11_4_1_2_12_DHA.RTF
12.1	Total extent of exposure to the study drug [Safety Set]	12_1_a_expos.RTF
12.2.1	Summary of adverse events [Safety Set]	12_2_1_ae_overview.RTF
12.2.2	Number of patients with at least one treatment-emergent adverse event by MedDRA primary system organ class and preferred term [Safety Set]	12_2_2a_tae_socpt.RTF
12.2.2	Number of patients with at least one related treatment-emergent adverse event by MedDRA primary system organ class and preferred term [Safety Set]	12_2_2b_relteae_socpt.RTF
12.3.1.1	Listing of deaths [Safety Set]	12_3_1_1_deaths_list.rtf
12.3.1.2	Listing of serious adverse events [Safety Set]	12_3_1_2_sae_list.rtf
12.3.1.3	Listing of adverse events leading to definitive study treatment discontinuation [Safety Set]	12_3_1_3_aedefstoprt_list.rtf
12.4.2.2	Hematology: Number of patients with variations over time [Safety Set]	12_4_2_2_1Hem.RTF

SECTION	Title	RTF reference
12.4.2.2	Biochemistry: Number of patients with variations over time [Safety Set]	12_4_2_2_1Bioch.RTF
12.4.2.3	CNALV: Patients with haemoglobin < 10 g/dL and decreased from baseline >=2 g/dL (if baseline was measured) [Safety Set]	12_4_2_3a_hemog.RTF
12.4.2.3	CNALV: Patients with neutrophils < 1.5 G/L or WBC < 3G/L (if neutrophils missing) [Safety Set]	12_4_2_3b_neutr.RTF
12.4.2.3	CNALV: Patients with platelets < 100 G/L [Safety Set]	12_4_2_3c_plat.RTF

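### Cardioversion success is compared between arms on the FAS, which admits only successfully cardioverted patients, so ECV failure and the secondary objective on ECV efficiency cannot be assessed

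*SAP*

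**What the plan says.** The SAP's study objectives (section 6) list as a secondary objective "the efficacy of F373280 on the efficiency of direct ECV". The section that serves it is 14.2.5.5, which describes by arm and compares by country-stratified CMH test "The number of spontaneous cardioversion before visit 3, of successful cardioversion (including number of shocks distribution) at visit 3", together with the number of patients who needed a further cardioversion after the initial ECV.

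The analysis set is fixed in two places. Section 14.2 states "All secondary analyses will be performed on the FAS", with no exception. The Appendix 5 table list carries the same label, in a title beginning "Cardioversion assessment- [FAS".

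Section 7 defines the FAS as randomised patients who took at least one dose "and with a successful cardioversion observed at visit 3". Success means spontaneous conversion before V3 or a successful ECV at V3, and "early relapse within the observation period after ECV will be considered as non successful". Section 18 notes that "the Full Analysis Set definition was clarified with the definition of successful cardioversion" and makes no exception for 14.2.5.5. The wider set in section 7 is the Safety Set, "composed of all randomised patients having taken at least one dose of the study treatment".

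**The concern.** The entry condition of the analysis set is the outcome being compared. A patient whose ECV failed, or who relapsed within the observation period, is not in the FAS, so the table that should show whether the drug affects ECV success contains no failures.

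Treatment starts 4 weeks before ECV (section 6, Study treatment), so cardioversion success is a post-randomisation outcome that the drug may change. Spontaneous conversion and the shock distribution are therefore also compared only among patients selected on a possible treatment effect, and can differ between arms for that reason alone.

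At stake is the planned answer to a stated secondary objective. The result could be empty, or it could be a computable figure that points the wrong way. The number needing another cardioversion after the initial ECV is a coherent FAS quantity and is not part of this concern.

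**Working it through.** The SAP gives no figure for this comparison and no spontaneous-conversion or ECV-success rates. Steps 1 and 2 need no rates. Steps 3 to 6 use assumed rates and only illustrate size.

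**1. Who is in the FAS.** By section 7, each FAS patient is either a spontaneous converter or a V3 ECV success. Failed ECV, early relapse and no cardioversion are all outside.

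**2. What the success comparison can then be.**
- *Reading A: overall success, or success among attempted ECVs.* Both are 100% in each arm. Every country stratum has an empty failure column, so the CMH numerator is 0 and its variance is 0: the statistic is 0/0.
- *Reading B: V3 ECV successes over all FAS patients.* The test is defined, but within every stratum ECV success is the complement of spontaneous conversion. The two tests are the same test.

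**3. Size under assumed rates.** Let s be the spontaneous-conversion rate (same in both arms) and S overall success, and assume ECV is attempted in everyone without spontaneous conversion.
- Success among attempts = (S − s)/(1 − s)
- FAS, reading B = (S − s)/S
- FAS spontaneous share = s/S

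For s = 10%: S = 95% gives 0.85/0.90 = 94.4%, 0.85/0.95 = 89.5% and 0.10/0.95 = 10.5%. S = 85% gives 0.75/0.90 = 83.3%, 0.75/0.85 = 88.2% and 0.10/0.85 = 11.8%.

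| Assumed s; S by arm | Among attempts | FAS, A | FAS, B | FAS spontaneous |
|---|---|---|---|---|
| 5%; 95% v 90% | 94.7% v 89.5% (5.3 points) | 100% v 100% | 94.7% v 94.4% (0.3) | 5.3% v 5.6% |
| 10%; 95% v 85% | 94.4% v 83.3% (11.1) | 100% v 100% | 89.5% v 88.2% (1.2) | 10.5% v 11.8% |
| 20%; 95% v 75% | 93.8% v 68.8% (25.0) | 100% v 100% | 78.9% v 73.3% (5.6) | 21.1% v 26.7% |

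The last column shows a false difference in spontaneous conversion, since s is equal in both arms. At the low end it is 0.0029 × about 61 FAS patients per arm (135/2 × 0.90) = 0.2 of a patient.

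**4. Sign reversal on reading B.** Assume spontaneous conversion 20% v 10% and ECV success among attempts 90% v 80%, so the first arm is better on both. Overall success is 0.20 + 0.80 × 0.90 = 92% v 0.10 + 0.90 × 0.80 = 82%. The FAS ECV share is 0.72/0.92 = 78.3% v 0.72/0.82 = 87.8%: the better arm looks worse.

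**5. Whole-patient check.** Suppose all 135 randomised patients were treated (68 v 67), with 14 v 7 spontaneous conversions and ECV success in 49/54 v 48/60 (90.7% v 80.0%). The FAS holds 63 v 55. Reading B gives 49/63 v 48/55 (77.8% v 87.3%). Unstratified Mantel-Haenszel: expected 63 × 97/118 = 51.79; variance 63 × 55 × 97 × 21/(118² × 117) = 4.33; chi-square (49 − 51.79)²/4.33 = 1.794. Spontaneous conversion, 14/63 v 7/55, gives the same 1.794.

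**6. What the full denominator could show.** With about 67 treated per arm (135/2 = 67.5), a 5% two-sided normal-approximation test of overall success has power of 37% for 90% v 80%, 63% for 90% v 75% and 75% for 95% v 80%. On the FAS each of these is 100% v 100%.

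**The case against.** The strongest counter-arguments are these.

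- *The objective is not defined as success rate alone.* The shock distribution and repeat cardioversion also bear on ECV efficiency and vary within the FAS. That stands as far as it goes: shocks among successes can be tabulated and tested. But the comparison is conditional on success and leaves out the patients in whom shocks did not work, so it cannot stand in for a success comparison.
- *The misleading result needs reading B.* Given the definition of success in section 7, reading A is the more natural one, and its failure is obvious once the table is run. This is fair. The sign reversal is conditional on reading B, but reading A leaves no comparison at all.
- *The counts can be recovered.* Overall success by arm can be rebuilt from the Safety Set and FAS counts planned in section 12. ECV success among attempts might be rebuilt from the exclusion reasons in section 9, if these separate a failed ECV from one not attempted; that list is in a separate document not shown. No planned efficacy analysis does either.
- *The endpoint is exploratory.* Section 8 says so for everything except the primary test. This limits the severity but does not make the table informative.
- *The illustrative rates are chosen.* True, and the smallest distortion is trivial. The structural result does not depend on them.
- *Section 7 assigns efficacy to the FAS and safety to the Safety Set.* Section 14 already lets individual analyses depart from the FAS, and section 13 already uses the Safety Set for demographics, so this is no bar to the change.

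**Conclusion.** The concern holds. As written, the SAP removes every ECV failure and early relapse before comparing cardioversion success, so the success comparison is either undefined (100% v 100%) or a restatement of spontaneous conversion with its sign reversed. The objective on ECV efficiency has no planned analysis that can answer it. This follows from the definitions alone.

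The size cannot be known from the document. Over the assumed range (spontaneous conversion 5% to 20%, equal in both arms; overall success from 95% v 90% to 95% v 75%; ECV attempted in all others), a difference among attempts of 5.3 to 25.0 points appears as 0, or as 0.3 to 5.6 points. With unequal spontaneous conversion its direction can reverse. The primary analysis and the sample size are unaffected. This should be fixed, but it does not threaten the trial's main conclusion.

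**What to change.** In section 14.2.5.5 and the Appendix 5 title:

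- Analyse spontaneous conversion before V3 and overall cardioversion success on all randomised treated patients (the Safety Set), and state how patients who leave before V3 are counted.
- Report ECV success, and number of shocks where recorded, among all patients in whom ECV was attempted at V3, including failures and early relapses. Note beside it that this denominator is itself post-randomisation, because ECV is done only without spontaneous conversion and with a stabilised INR.
- Keep the number needing another cardioversion on the FAS; add patients with a failed ECV only if those data were collected.
- Reword section 14.2 so that the FAS is the default from which a subsection may depart, as the opening of section 14 already allows.

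The cost is SAP wording and one table shell, plus two data checks: whether shock counts were recorded for failed ECVs, and whether later cardioversions were collected after a failed ECV. The second matters because section 6 describes the 20-week follow-up only after a successful ECV or spontaneous conversion.

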### **Study treatment**

After a 1 to 4-week run-in period, patients are randomised into one of the following treatment groups: F373280 1g or placebo 1g for 24 weeks. The treatment starts 4 weeks before ECV and ECV is performed in patients with no spontaneous cardioversion and with INR levels stabilized as mentioned in the protocol. The follow-up is of 20 weeks after a successful ECV (at visit 3 – cardioversion visit) or after a spontaneous CV.

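### Repeat cardioversion is counted only after an initial ECV but compared on the whole FAS, so the comparison is tilted if spontaneous conversion differs between arms

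*SAP*

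**What the plan says.** SAP section 14.2.5.5 (Cardioversion assessment) lists three items: spontaneous conversions, successful cardioversions at V3, and repeat cardioversions. For the third it states that "the number of patients needing another cardioversion after initial ECV will be described by treatment group and compared using Cochran-Mantel-Haenszel test stratified by country". The section gives no denominator of its own.

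The denominator comes from elsewhere. Section 14.2 states: "All secondary analyses will be performed on the FAS". The table list in Appendix 5 also labels the cardioversion output as an FAS table.

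Two other sections determine who is in that set and who can have an initial ECV:

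- Section 7, in the FAS definition: "A successful cardioversion will be defined as either spontaneous cardioversion before V3 or successful ECV performed at V3". Both routes to sinus rhythm qualify.
- Section 6, Study treatment: "ECV is performed in patients with no spontaneous cardioversion". A spontaneous converter therefore has no ECV at V3.

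Nothing in the SAP restricts the repeat-cardioversion item to patients who had an ECV. Nothing says how a first ECV given later to a spontaneous converter is to be counted.

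**The concern.** Take two FAS patients with the same course after V3: each relapses and is cardioverted once. The one who had an ECV at V3 meets the definition of the event. The one who converted spontaneously does not, because there was no initial ECV for the later one to follow. Both stand in the denominator of the same test.

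This matters for a treatment comparison because the route to sinus rhythm is settled after randomisation. Section 6 says "The treatment starts 4 weeks before ECV", so the drug has time to affect spontaneous conversion, and section 14.2.5.5 itself compares spontaneous conversion between arms. If one arm has more spontaneous converters, more of its later cardioversions go uncounted. Part of the conversion result then reappears as an apparent reduction in repeat cardioversion.

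**Working it through.** **Plan's own figure.** The SAP gives no expected rate of spontaneous conversion or of repeat cardioversion, so there is no figure to reproduce for this item. The rates below are assumptions.

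**Symbols.** In each arm, s is the share of FAS patients who converted spontaneously, r_E the risk of a later cardioversion in V3-ECV patients, and r_S that risk in spontaneous converters. Assume no drug effect on r_E or r_S, and at most one later cardioversion per spontaneous converter.

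- True proportion with a cardioversion after V3: (1 − s) × r_E + s × r_S
- Proportion counted as the SAP is written: (1 − s) × r_E
- Proportion missed: s × r_S

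The artefact in the placebo-minus-active difference is therefore r_S × (s_active − s_placebo). It is zero when s is equal in the two arms, or when spontaneous converters are never cardioverted later.

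**Equal later risk (r_E = r_S = r).** The true relative risk is 1.00. The counted relative risk is (1 − s_active)/(1 − s_placebo), whatever the value of r. With r = 30%:

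| s, placebo v active | Counted, placebo | Counted, active | Gap | Spurious RR |
|---|---|---|---|---|
| 5% v 5% | 0.95 × 0.30 = 28.5% | 28.5% | 0 | 1.00 |
| 5% v 10% | 28.5% | 0.90 × 0.30 = 27.0% | 1.5 points | 0.95 |
| 10% v 20% | 27.0% | 0.80 × 0.30 = 24.0% | 3.0 points | 0.89 |
| 15% v 30% | 0.85 × 0.30 = 25.5% | 0.70 × 0.30 = 21.0% | 4.5 points | 0.82 |

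**In patients.** The SAP does not give the FAS size. Applying its 15% planning rate for non-assessable patients to the 135 randomised gives 135 × 0.85 / 2 = 57.4, or about 57 per arm. The last three rows then correspond to 16.2 v 15.4, 15.4 v 13.7 and 14.5 v 12.0 patients: gaps of about 0.9, 1.7 and 2.6.

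**Effect on the test.** With 57 per arm, a two-sided 5% normal approximation without stratification was applied for r from 20% to 50% and unequal s from 5% v 10% up to 10% v 30%. The spurious gap was 1 to 10 points and the chance of p < 0.05 was 5.2% to 19.2%. At r = 30% and s = 10% v 20% the chance was 6.5%.

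**Lower risk in spontaneous converters.** Let r_E = 30%, r_S = 15% and s = 10% v 20%.

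- True, placebo: 0.90 × 0.30 + 0.10 × 0.15 = 28.5%
- True, active: 0.80 × 0.30 + 0.20 × 0.15 = 27.0%
- Counted: 27.0% v 24.0%

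The gap grows from 1.5 to 3.0 points. The artefact is half of that under equal risk (0.15 × 0.10 = 1.5 points), so it does not depend on equal risk, though it shrinks with r_S.

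**After the fix.** Counting any cardioversion after V3 in all FAS patients removes the artefact in every scenario. Under equal risk the gap is 0 and the relative risk 1.00.

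**The case against.** The best defence is that the item presupposes an initial ECV, so a patient without one is not applicable rather than a non-event. The shock distribution at V3, in the same sentence, likewise has meaning only for ECV patients yet sits under the same FAS label. Alternatively, initial ECV may loosely mean V3, since sections 6 and 14.1 use the ECV visit as another name for V3. On that reading there is no artefact.

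Either may have been intended, but the SAP states neither. The first would compare subsets formed after randomisation; the second needs different wording before a programmer would code it that way.

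Several points on this side stand:

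- The sizes rest wholly on assumed rates, and each unequal scenario puts more spontaneous conversion on active.
- Section 8 makes every result other than the primary test exploratory, and spontaneous conversions are tabulated by arm alongside, so an imbalance would be visible.
- Section 6 names the efficiency of direct ECV as a secondary objective, and a count after initial ECV serves it.
- Broadening the count does not give a fully randomised comparison, because the FAS is itself selected on conversion at V3.

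A reader might infer that spontaneous converters can never score an event and that the arm with more of them automatically looks better. The documents do not support that. If initial ECV were read as a patient's first ECV at any time, a spontaneous converter with two later ECVs could be counted. The tilt also needs conversion rates that differ between arms, which the SAP does not report.

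**Conclusion.** The point holds as a defect in how a secondary, exploratory comparison is defined. On the natural reading, section 14.2.5.5 keeps spontaneous converters in the denominator but does not count their first later cardioversion. This also fits poorly with section 14.1, which follows these patients for recurrence from V3 as it does the others.

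If spontaneous conversion differs between arms and the later risk is equal, the spurious relative risk is 0.95 to 0.82 over the three unequal scenarios tabulated, or about one to three patients per arm at an assumed 57 per arm. If conversion is equal between arms, later cardioversions are undercounted but neither arm is favoured. The primary analysis and its conclusion are not touched. The correction is worth making because a test is planned and its result could be misread as fewer repeat cardioversions on one arm.

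**What to change.** Replace the third item in section 14.2.5.5 with two:

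1. *For the country-stratified Cochran-Mantel-Haenszel comparison:* the number of FAS patients with at least one cardioversion after V3, whether sinus rhythm at V3 was reached by ECV or spontaneously, with all FAS patients in the arm as denominator.
2. *Descriptive only:* the number of patients with a further cardioversion after the V3 ECV, with FAS patients who had an ECV at V3 as the stated denominator. This keeps the information relevant to the direct-ECV objective without testing a subset formed after randomisation.

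The cost is a short text change, one changed flag and one extra table row; the change should also be listed in section 18. There is a small downside: the tested item becomes slightly broader than the one now named. The sponsor must also confirm that cardioversions after V3 were recorded for spontaneous converters, which the SAP does not show. The change concerns counting only and does not affect patient management.
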